## METHOD

### **Study Design**

The study was a randomized, double blinded, placebo-controlled trial with 4-week intervention followed by a two-month open label follow-up period. This study was approved by the University of Utah Institutional Review Board (IRB\_00165943) and registered on clinicaltrials.gov (<https://clinicaltrials.gov/study/NCT05952297>).

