### **Procedure**

All study procedures were performed remotely. Interested participants completed a screening survey, then if eligible, a study coordinator contacted the participant via email to review study information and schedule a time to complete informed consent. Upon completion of informed consent, study materials were sent to the participant that consisted of the Evolv28 device (inactive), a Fitbit and device instructions. Upon receipt of the study materials, participants completed an instructional meeting with study staff, where they reviewed baseline procedures and Fitbit setup. Participants then completed online surveys, 7 days of daily electronic sleep diary surveys (SurveySignal) and wore the Fitbit for 7 days.

After participants completed their baseline week, a staff member, who was not associated with the study, determined each participant's group assignment and then sent that participant's device serial number to programmers. Participants were randomized 1:1 between intervention and control groups. The randomization table was generated using a random number table stratified by gender using permuted blocks of 4 to 6 participants. Study staff and participants were both blinded to treatment group assignment. To begin the 4-week trial period, the study coordinator met with each participant to ensure the device was activated and confirmed the participant's understanding of how to use it. The intervention

group received the active program, and the control group received an inactive program. In both conditions, the device and application appeared to be active. Participants were asked to wear the device for at least 3 hours per day. If any technical issues occurred, the intervention time was extended to allow for at least four weeks of use before the post-intervention assessment. Participant adherence to the Fitbit and Evolv28 were monitored by the study statistician throughout the trial and reminders were sent to participants who were non-adherent in wearing either device for more than 2 days.

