For the follow-up assessment, participants wore the Fitbit again for 7 days and completed electronic sleep diaries for 7 days. Upon completion of the 4-week trial, participants completed a set of follow-up surveys to assess changes in sleep and mood. After the post-trial assessment, all Evolv28 were transitioned to run the active treatment program between week 4 and 3 months. At the end of 3 months, participants completed online questionnaires. Participants were compensated with \$100 via an Amazon.com gift card and kept the study Fitbit and Evolv28 device.

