#### Data analysis

Data were analyzed using R version 4.2.2. We utilized descriptive statistics to describe the sample statistics at baseline. Then, we conducted linear mixed models to the effect for time and time x group interaction. The primary outcome was defined as change in ISI at 1-month. We also conducted linear mixed models to examine change over time and time x group changes from baseline to 3-months. Analyses were conducted as intention to treat and all participants who completed baseline data and were randomized were included in the mixed models. We utilized chi-square tests to evaluate percentage with a response to the intervention (decrease of 6 points or more on the ISI) and remission (ISI post-intervention score  $\leq 7$ ). An a-priori power analysis, assuming a medium-to-large effect size of  $d = 0.74$ , indicated that a total sample size of 60 participants (30 per group) would provide a power of 80% to detect significant differences with a two-sided alpha level of 0.05.

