Functional Outcomes of Sleep	32.8	3.85	34.6	5.9	+1.8 a	+2.07	31.8	5.6	35.2	5.4	+3.4 a	-0.13	0.319	0.004		
Patient Health Questionnaire	7.4	3.64	7.1	4.8	-0.3 a	+1.20	7.6	3.6	5.4	4.7	-2.2 a	+1.09	0.111	0.007		

Note. Missing data n=1 at the 3-month assessment.  $P_{between}$ = *p* value for the time x condition effect,  $p_{within}$ = *p* value for the time effect.

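### The 3-month time x group test compares immediate with delayed active use, so a null result there does not refute efficacy, and the 3-month time effect has no concurrent control

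*Combined protocol and SAP*

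**What the plan says.** Study Design describes a blinded, placebo-controlled trial with "4-week intervention followed by a two-month open label follow-up period". Under Procedure, "Participants were randomized 1:1 between intervention and control groups". For the four weeks the intervention arm ran the active program and "the control group received an inactive program". Once the post-trial assessment was done, "all Evolv28 were transitioned to run the active treatment program between week 4 and 3 months". The last assessment follows that period: "At the end of 3 months, participants completed online questionnaires".

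Data analysis places the primary endpoint before the switch: "The primary outcome was defined as change in ISI at 1-month". It then adds mixed models to "examine change over time and time x group changes from baseline to 3-months", without saying what the group term means once both arms are on the active program.

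Table 4 reports these models under the column headings Intervention and Control. Its two p-value columns, p_between (time x condition) and p_within (time), carry the same names and definitions as in Table 2, the blinded 1-month table. Neither the table nor its note mentions the switch.

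**The concern.** The same label covers two different comparisons. At 1 month p_between compares active with inactive. At 3 months it compares about three months of active use with about two months of active use preceded by an inactive month. If a device effect is largely reached within two months of use, both arms have it by month 3 and the expected interaction is near zero, however well the device works.

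The time effect has a different problem. Every participant is on the active program after week 4, and entry required an ISI of at least 15. A fall from baseline to 3 months therefore combines any device effect with placebo response, regression to the mean and natural course, and no untreated arm separates them.

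The Table 4 ISI row shows what is at stake: changes of -7.98 (Intervention) and -9.31 (Control), p_between 0.360, p_within 0.001. It could be read as no benefit over control at 3 months, or as a lasting benefit of the device. The design supports neither reading.

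**Working it through.** **1. The plan's own figure.** Inputs from Data analysis: d = 0.74, two-sided alpha 0.05, power 80%, 30 per group. By the normal approximation, n per group = 2(1.960 + 0.842)² / 0.74² = 28.7, so 29. The two-sample t-test gives 29.66, so 30 per group, and power of 80.5% at 30. The stated figure reproduces. It is not tied to the 3-month contrast.

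**2. Power at 3 months as a function of catch-up.** Let f be the share of a between-arm difference of d = 0.74 that remains at 3 months, after controls have also had the active program. The documents give no value for f, so it is an assumption and is shown over its range. The noncentrality is f × 0.74 × √(30/2) = f × 2.866, with 58 degrees of freedom.

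| f | remaining d | power |
|---|---|---|
| 1 | 0.74 | 80.5% |
| 0.75 | 0.555 | 56.1% |
| 0.5 | 0.37 | 29.1% |
| 0.25 | 0.185 | 10.9% |
| 0 | 0 | 5% (alpha) |

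**3. Why f cannot be fixed from the documents.** Suppose benefit builds linearly with time on the active program, and take 4 weeks as one third of the 3 months.

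- If 0.74 is the 4-week effect and growth continues, the immediate arm is at 3 × 0.74 and the delayed arm at 2 × 0.74 at month 3. The gap is still 0.74, so f = 1. With 28 and 30 analysed, power is about 79%.
- If 0.74 is instead the effect reached only after 3 months, the gap at month 3 is 0.74 / 3 = 0.247, and power at 28 and 30 is 15.2%.

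The same growth pattern gives 79% or 15% depending on the time to which 0.74 belongs. (The arm of the one participant missing at 3 months is not stated, so 28 and 30 is itself an assumption.)

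**4. The post-switch change as an alternative contrast.** From the ISI means in Tables 2 and 4:

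- Control: 11.0 to 9.3, a change of -1.7.
- Intervention: 11.8 to 11.2, a change of -0.6.
- Difference: 1.1 points.

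No standard error is given. Assuming a change SD of 4 to 6 points (not in the documents), SE = SD × √(1/28 + 1/30) = about 1.1 to 1.6.

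The expected value of this contrast also depends on the growth pattern. With linear build to a full effect D at 3 months, the immediate arm goes from D/3 to D and the delayed arm from 0 to 2D/3. Both gain 2D/3, so the expected difference is 0, while the planned baseline-to-3-month contrast keeps D/3. The post-switch contrast is informative only if the immediate arm has largely plateaued by week 4.

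**5. Information from the later visit.** The Table 2 note gives 3 + 2 = 5 missing questionnaires at 1 month. The Table 4 note reads "Missing data n=1 at the 3-month assessment". If both counts refer to the 59 participants in Table 1, at least 5 - 1 = 4 of those missing at 1 month returned at 3 months.

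**The case against.** The design is openly described: the follow-up is called open label, the switch is stated, and the primary endpoint precedes it. The table notes define both p-values neutrally, and nothing in the document draws an efficacy or durability conclusion from the 3-month results. All of this stands. It limits the point to a secondary analysis and to how its results may be interpreted.

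Three stronger readings are tempting, and the documents support none of them.

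- A reader might infer that the 3-month interaction is invalid, or can never show a device effect. If the device does nothing, randomisation still makes it a valid test, and a lasting advantage for the early starters would be indirect evidence of an effect. In the printed ISI means the difference runs the other way: -9.31 against -7.98, or 1.33 points in favour of the delayed arm.
- A reader might infer that power at 3 months is known to be low, say 15% or 5%. Those values need 0.74 to be a 3-month effect, or full catch-up. The documents state neither, and other assumptions give about 80%.
- A reader might infer that the post-switch change should replace the planned contrast. It can have expected value zero where the planned contrast does not. It is also open-label, starts from a post-randomisation visit with different missingness, and would be chosen after the results were available. The 1.1-point difference is about the size of its own assumed standard error.

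**Conclusion.** The point holds as one of estimand and labelling. The 3-month time x group test is a randomised comparison of immediate with about 4-week-delayed active use. A null p_between at 3 months does not refute efficacy, because power against a true d of 0.74 with 30 per group could lie anywhere from 5% to about 80%, depending on a catch-up share that the documents do not give. That range assumes that catch-up only narrows the gap and approximates the mixed-model interaction by a two-sample t-test. The conclusion that p_within at 3 months has no concurrent control needs no numerical assumption. The primary 1-month contrast precedes the switch and is not invalidated.

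**What to change.** - Fit one mixed model with baseline, 4 weeks and 3 months as categorical visits by arm, and draw efficacy conclusions from the 4-week contrast only. Participants who missed 1 month but returned at 3 months then inform the 4-week estimate, under the usual missing-at-random assumption.
- Keep the baseline-to-3-month contrast, but define it as immediate versus delayed start, head the Table 4 columns active-active and sham-active, and treat it as descriptive.
- State in the Table 4 note that all devices ran the active program after week 4 and that p_within is uncontrolled.
- The between-arm difference in change from 4 weeks to 3 months may be added as an exploratory open-label contrast, with its confidence interval and a statement that it is informative only if the immediate arm has largely plateaued by week 4. It should not replace the planned contrast.

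Because results are already tabulated, the revised text should say that the relabelling and any added contrast were specified after the fact. The cost is one refitted model on existing data and edits to the analysis section and Table 4. The downside is that the 3-month results become descriptive.

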## Figure Captions

**Figure 1**

CONSORT Flowchart of Participants

**Figure 2**

Response and Remission

*Note.* Response and remission scores of participants are shown for control and intervention groups. Response is a clinically meaningful reduction in Insomnia Severity Index score (change of 6 or more) from screening to end of the 1-month trial. Remission is an Insomnia Severity Index score of 7 or below at the end of the 1-month trial.

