### **Participants**

Participants were recruited from the United States via social media advertising and the University of Utah research study locator portal. Inclusion criteria included the following: age 18-65, read and write in English, smartphone user and reporting moderate to severe insomnia symptoms, defined as an

Insomnia Severity Index score of  $\geq 15$ . Participants were excluded if they had diagnosed sleep disorders other than insomnia (e.g., sleep apnea or restless legs syndrome) or were currently receiving additional treatment for insomnia (e.g., hypnotic medication, cognitive behavioral therapy, etc.). Further exclusion criteria include a history of serious mental health conditions (e.g., Patient Health Questionnaire 8 score of  $>15$ , psychosis, Bipolar I or the use of antipsychotic or mood stabilizing drugs), serious physical conditions (e.g., current cancer treatment, neurological illness), drug use (as defined by  $>14$  alcoholic beverages per week, the use of cannabis  $>3$  times in the past month, any use of illicit street drugs), caffeine intake of  $>400$ mg per day, overnight work more than once a month, frequent moderate to severe migraine attacks or headaches, pregnancy, and traveling across time zones  $>3$  times throughout the study period.

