Patient Health Questionnaire	7.40	3.6	5.4	3.6	-2.00 a	-0.07	7.7	3.6	4.7	3.4	-2.99 a	-0.23	0.39	0.001		

Note. Missing questionnaire data  $N=3$  in the intervention group and  $N=2$  for the control group.  $P_{between}=p$  value for the time x condition effect,  $p_{within}=p$  value for the time effect.

Table 3. Fitbit and Sleep Diary Outcomes at 1 Month

Assessment	Intervention						Control						$p_{between}$	$p_{within}$		
	Baseline		1-month		Change		Baseline		1-month		Change					
	M	SD	M	SD	M	SD	M	SD	M	SD	M	SD				
Sleep diary																
Sleep duration (h)	6.36	1.77	6.89	2.08	+0.53 a	+0.30	6.36	1.5	6.64	1.86	+.28 a	+0.34	0.25	0.046		
Wakefulness after sleep onset (m)	34.8	53.4	28.8	49.8	-6.0	-3.39	29.3	44.4	31.8	42.0	+2.4	-2.67	0.37	0.73		
Efficiency (%)	75.0	0.16	79	0.15	+0.04	-0.01	78.0	0.14	77.0	0.16	-0.01	+0.02	0.03	0.90		
Sleep latency (m)	43.2	46.2	39	42.0	-4.2	-4.69	41.4	41.4	43.2	52.2	+1.8	+10.70	0.07	0.63		
Fitbit																
Sleep Duration (h)	6.28	0.58	6.47	1.02	+0.19	+0.43	6.37	0.88	6.47	1.45	+0.1	+0.57	0.80	0.70		
Wake after sleep onset (m)	48.8	8.1	51.4	17.7	+2.6	+9.60	50.9	17.2	49.8	16.9	-0.9	-0.33	0.46	0.74		
Efficiency (%)	93.6	2.6	92.9	5.8	-0.7	+3.22	93.9	2.4	94.1	2.80	+0.2	+0.34	0.55	0.81		

*Note.* Missing data for actigraphy (n=23), missing data for sleep diaries (n= ).  $p = p_{between} = p$  value for the time x condition effect,  $p_{within} = p$  value for the time effect.

Table 4. Results of Self-Reported Outcomes at 3-Months

Assessment	Intervention						Control						$p_{between}$	$p_{within}$		
	Baseline		3-month		Change		Baseline		3-month		Change					
	M	SD	M	SD	M	SD	M	SD	M	SD	M	SD				
Insomnia Severity Index	19.1	3.3	11.2	4.7	-7.98 a	+1.36	18.6	3.2	9.3	4.5	-9.31 a	+1.29	0.360	0.001		
PROMIS Sleep Disturbance	60.6	5.9	53.7	8.0	-6.84 a	+2.16	60.8	4.9	52.4	6.5	-8.37 a	+1.67	0.478	0.001		
PROMIS Sleep-Related Impairment	61.0	6.1	56.2	9.4	-4.81 a	+3.30	60.4	6.2	52.6	9.1	-7.84 a	+2.94	0.246	0.001		
General Anxiety Disorder	7.0	4.85	7.24	5.6	+0.24	+5.06	6.71	4.2	5.13	5.4	-1.58	+5.83	0.284	0.338		
Perceived Stress Scale	16.9	6.37	17.5	7.6	+0.6	+1.23	16.4	6.7	15.0	7.8	-1.4	+1.10	0.254	0.227		

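### Does it matter that Figure 2 counts ISI response from screening, Table 2 counts ISI change from baseline, and the response tests have no stated denominator?

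*Combined protocol and SAP*

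**What the plan says.** The Data analysis section sets the primary outcome: "The primary outcome was defined as change in ISI at 1-month". It then gives the responder analysis: "We utilized chi-square tests to evaluate percentage with a response to the intervention (decrease of 6 points or more on the ISI", with remission as a post-intervention ISI of 7 or below. Neither sentence names the starting score. The Figure 2 note does: response is a "reduction in Insomnia Severity Index score (change of 6 or more) from screening to end of the 1-month trial".

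The Procedure section describes two survey occasions before randomization. Before consent, "Interested participants completed a screening survey". After consent and shipment of the devices, "Participants then completed online surveys, 7 days of daily electronic sleep diary surveys (SurveySignal) and wore the Fitbit for 7 days". It does not list which questionnaires belonged to which occasion. The Participants section uses the ISI for entry: "reporting moderate to severe insomnia symptoms, defined as an" ISI of 15 or more.

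On the analysis set, the Data analysis section says: "Analyses were conducted as intention to treat and all participants who completed baseline data and were randomized were included in the mixed models". The note to Table 2 begins "Missing questionnaire data" and gives 3 participants in the intervention group and 2 in control. The Table 1 note gives arm sizes of 28 and 31.

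**The concern.** Screening and baseline are different moments in this trial, and the screening ISI is the one on which people were selected for scoring high. If the ISI was taken again in the baseline week, the second score would on average be lower through regression to the mean alone. Counting response from screening would then credit that fall to the trial period, and one participant could be a responder in Figure 2 yet fall short of 6 points on the scale used for the primary outcome.

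The second worry is the denominator. A mixed model keeps a participant who has no 1-month ISI, but a chi-square test needs a yes or no for each person counted. Naming only the mixed models in the inclusion rule leaves open whether percentages are out of 28 and 31 or out of those observed. At stake are the absolute response percentages, which readers tend to quote, and possibly the apparent difference between arms.

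**Working it through.** **1. Which reference Table 2 uses.** Intervention: 11.8 − 19.1 = −7.3 (printed −7.34). Control: 11.0 − 18.6 = −7.6 (printed −7.58). The tabulated change starts from the Baseline column, so the mismatch in labels is real.

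**2. Effect on response if there were two scores.** The printed change SDs cannot be used: 1.87 and 0.84 are simply differences of the two time-point SDs (5.2 − 3.3 = 1.9; 4.0 − 3.2 = 0.8). Assume a correlation of 0.5 between baseline and 1-month ISI.

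- SD of change, intervention: √(3.3² + 5.2² − 2×0.5×3.3×5.2) = 4.56
- SD of change, control: √(3.2² + 4.0² − 2×0.5×3.2×4.0) = 3.67

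With a screening score g points above baseline and a cut at 5.5 for whole-number scores, response is Φ((1.84 + g)/4.56) and Φ((2.08 + g)/3.67).

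| g | Intervention | Control | Arm difference |
|---|---|---|---|
| 0 | 65.7% | 71.5% | 5.8 points |
| 0.5 | 69.6% | 75.9% | 6.3 points |

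A half-point drop raises both arms by about 4 points and moves the difference between arms by half a point.

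**3. How large the drop could be.** A simulation took normally distributed applicant scores, rounded and limited to 0–28, selected at 15 or more, with an independent second measurement. Mean baseline-to-1-month improvement was set at about 7.5, with between-person SD 3. Applicant mean, SD and retest correlation r are assumptions. The re-measured baseline can be compared with Table 2 pooled over arms:

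- mean (28×19.1 + 31×18.6)/59 = 18.8
- SD √((27×3.3² + 30×3.2²)/57) = 3.25
- standard errors 3.25/√59 = 0.42 (mean) and 3.25/√(2×58) = 0.30 (SD)

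| Applicant mean, SD, r | Re-measured baseline (SD) | Response from screening / baseline | Gap (points) | Classified differently |
|---|---|---|---|---|
| 14, 5, 0.7 | 17.0 (4.1) | 76% / 66% | 10 | 22% |
| 16, 5, 0.8 | 18.4 (3.9) | 72.8% / 67.5% | 5.3 | 20% |
| 14, 5, 0.9 | 17.9 (3.4) | 74.1% / 70.0% | 4.1 | 16% |
| 16, 5, 0.9 | 18.8 (3.6) | 73.0% / 70.0% | 3.0 | 16% |
| 18, 4, 0.9 | 19.2 (3.3) | 72.7% / 71.3% | 1.4 | 14% |

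The first row does not fit this trial: its mean is about 4 standard errors too low and its SD nearly 3 too high. The other rows give about 1.5 to 5 points. Of the 25 + 29 = 54 participants inferred to have a 1-month ISI, 14–20% is about 8 to 11 people.

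If everyone improved by the same amount, applicant mean 16 and SD 5 give 3.9 points (r = 0.9) to 6.8 points (r = 0.8). That assumption implies a 1-month SD of 3.7 to 4.0, against 5.2 and 4.0 in Table 2.

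**4. One score or two.** With applicant mean 16 and SD 5, the selected screening score has mean 19.1 and SD 3.2, close to Table 2, while a re-measured score has SD 3.6 to 4.2. That leans towards a single score. A narrower applicant SD of 4 makes a re-measured score fit as well, so Table 2 does not settle it.

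**5. Denominator.** Observed: 28 − 3 = 25 and 31 − 2 = 29, if the missing questionnaires include the ISI. No response counts stand in the text, so take 16 and 20 responders for illustration (p uncorrected).

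| Rule for missing ISI | Intervention | Control | Difference | p |
|---|---|---|---|---|
| Observed only | 16/25 = 64.0% | 20/29 = 69.0% | −5.0 | 0.70 |
| Missing = non-response | 16/28 = 57.1% | 20/31 = 64.5% | −7.4 | 0.56 |
| Most favourable to intervention | 19/28 = 67.9% | 20/31 = 64.5% | +3.3 | 0.79 |
| Least favourable to intervention | 16/28 = 57.1% | 22/31 = 71.0% | −13.8 | 0.27 |

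For remission, with 5 and 6 remitters assumed, the difference runs from −7.9 to +9.2 points, with p no lower than 0.41.

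**The case for a change.** The strongest case for acting is reproducibility. Response and remission have their own planned tests and their own figure, and the note to that figure presents the 6-point fall as clinically meaningful. Someone holding the data could not be sure of regenerating the percentages without asking which pre-treatment score was used and how five missing people were handled. The general intention-to-treat statement does not answer the second question, because it does not say whether a missing ISI is a failure, is imputed or is left out. In the illustration the sign of the arm difference changes with the rule. The repair would also be short.

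Most of this stands as a remark on reporting. It is weaker as a criticism of the analysis. The Figure 2 note does name a reference, and the silence in the Data analysis section does not contradict it; the open question is only whether screening and baseline are one score. The images of Figures 1 and 2 are not available here and may print counts and denominators. The sign changes only under opposite extreme codings of the two arms, around a difference already close to zero. Counting missing as non-response is one acceptable rule among several, so the text does not depart from a single correct choice.

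**Conclusion.** No change to the plan follows. The reference-point issue is at most a few percentage points on a secondary, descriptive percentage: zero if the ISI was taken once, about 1.5 to 5 points if it was repeated and the applicant pool resembled Table 2, and up to about 7 if improvement were uniform. Selection preceded randomization, so the inflation falls on both arms alike and has no known direction between them. Remission depends only on the final score. The primary comparison uses the Baseline column throughout, and its time-by-group p-value of 0.88 owes nothing to the Figure 2 definition.

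The denominator is a detail that an analyst working under intention to treat would settle and report. With 3 of 28 and 2 of 31 missing, the largest possible movement is 10.7 and 6.5 points in the arm rates, and no illustrative coding approaches significance.

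This rests on assumed applicant distributions, retest correlations and responder counts, since the text gives none, and on reading the missing questionnaires in the Table 2 note as including the ISI. Using one label for the starting score in Figure 2 and Table 2 is an editorial matter.
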